LFV is now considered among the top 10 risk factors for the development of NCDs and overall mortality (9). Alarmingly, in the USA only 40% and 7% of children meet the U.S. Department of Agriculture Food Patterns fruit and vegetable intake recommendation, respectively (10). It is not known if a polyphenol rich intervention with wild blueberry can improve markers of immune, cardiovascular and bone health in children with low fruit and vegetable consumption (LFV). Data from ACNC suggest that fitness (peak VO2) modifies the association between fruit and vegetable (FV) consumption and vascular health of children. Specifically, children with combined low FV intake and low peak VO2 have higher blood pressure values than children with low fitness but higher FV consumption. These results suggest, that children with low fitness would not only benefit from more exercise but also from a higher FV content in their diets. However, higher quality evidence is needed to inform clinical practice and dietary guidelines.

Objectives

- 1) Characterize plasma and urine profile of polyphenol-derived metabolites of schoolage children supplemented short-term with wild blueberry powder.
- 2) Assess the effects of short-term wild blueberry supplementation on immune responses as well as on markers of bone metabolism and cardiovascular health in apparently healthy children who consume ≤2 cups of fruits and vegetables per day.
- 3) Evaluate if cardiorespiratory fitness (peak VO2) modifies the association between blueberry derived polyphenol consumption and markers of cardiovascular health.

Study Design and Procedures

This is a double-blind randomized control trial aiming to characterize the profile of polyphenol-derived metabolites in plasma and urine of children ages 11 to 12 years supplemented short-term with wild blueberry powder. Further, the study will assess if a short-term supplementation (up to 6 days) with wild blueberry powder impacts immune responses as well as markers of cardiovascular and bone health while assessing for the effect modification of peak VO2. Up to 44 children (boys and girls) will be recruited to participate. After telephone screening, the children and parents will come to

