Stool, urine, and saliva collection		X	X
Endothelial function		X	X
Blood draw		X	X

others). All participants will be instructed to follow a low polyphenol diet (a sample meal plan will be provided). Participants will start the low polyphenol diet 2 days prior to visit #2 up until the day prior to visit #3 (total of 7 consecutive days on a low polyphenol diet).

Title: The Blueberry Study

PI: [name] M.D.

Participants will still be eligible if they consume less than or equal to two (2) cups of fruits and vegetables combined per day before Visit #2. Visit 3 will continue even if the participant did not adhere to the low polyphenol diet.

Wild blueberry/placebo intervention: wild blueberry containing foods (i.e., wild blueberry powder or wild blueberry extract) or identical placebo-containing foods will be consumed starting on the day of study visit #2 until the morning of visit #3 (total of 6 days on blueberry or placebo). These food items have been designed in collaboration with the University of Arkansas Department of Food Science and may consist of oatmeal bars, beverages, ice pops, and cookies. Participants will receive product combinations that deliver up to 30g of wild blueberry powder per day (or the equivalent anthocyanin content in the case of products containing wild blueberry extract) or placebo. Parents and participants will keep a daily log which will be used to assess compliance with blueberry/placebo containing products and low polyphenol diet. Research staff may contact study participants between visits via phone, email, or text to inquire about their experience, perceived barriers with adhering to the intervention and to their goals. Participants will be asked to complete the Study Product Log book of what was consumed.

Study Diet Coaching: Participants will be educated by a trained nutritionist on how to avoid polyphenol rich foods. A sample low polyphenol meal plan will be provided to the participants if needed.

Medical History: an interviewer-administered medical history questionnaire will be conducted.

Anthropometrics: Anthropometric measurements (body weight, height, waist and hip circumference) will be obtained using standardized techniques, while the children are wearing light clothing and without shoes. All anthropometric measures will be made in duplicate, or triplicate if not within acceptable agreement.

[figure not shown]

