Body Composition: Body composition will be assessed using Dual-Energy X-ray Absorptiometry (DXA; Horizon-A with Advanced Body Composition™, Hologic, Bedford, MA). Measures of body composition are needed to standardize peak VO2 (see below) to lean body mass content. DXA technology involves very small amounts of ionizing radiation. Total body fat and fat free masses, bone mineral density, bone mineral content (whole body, femur,

and spine) will be determined. This will use the newest DXA technology (Analysis with InnerCore™ Visceral Fat Assessment) which can separate the adipose tissue depot into visceral and subcutaneous fat mass by performing a scan of <3 min.

Vital signs: Blood pressure, heart rate, and body temperature will be assessed using standard techniques at each visit.

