Stool, urine, and saliva sample collection: Stool samples will be collected and may be used to analyze the microbiome, polyphenol content, and polyphenol derived metabolites (table 1). Parents will be given the option to collect the child's stool sample at home. Instructions and supplies will be provided. Urine will be collected to measure wild-blueberry derived metabolites, markers of bone metabolism, and overall metabolic health. A urine sample will be collected the morning of visit #2. Urine will be collected before and following a single dose of blueberry or placebo containing foods on study visit #3. Saliva will be collected on visits #2 and #3 for metabolomics analysis. Supplies and instructions will be provided to participants.

Blood Collection After an overnight fasting, blood will be collected from a peripheral vein by a trained phlebotomist at visits #2 and #3. Up to 75 ml of blood will be collected during the entirety of the study. At visit #2, up to 16 ml (3.25 teaspoons) of whole blood will be collected following an overnight fasting. At visit #3, up to 24 ml (~1.6 tablespoons) of blood will be collected in the fasting state (baseline). After the initial blood draw, children will receive blueberry/placebo containing products. Participants will be free to drink water during this part. Eight ml (8 ml) of blood will be drawn 1 hour after the consumption of the study product while 6 ml will be drawn at 2, 3, 4, and 5 hours [Total 56 ml (24+ 32 mL) or 3.75 tablespoons on visit #3]. We may place a saline lock and administer a slow drip of saline

or lactate ringers at the first blood draw of visit #3 to minimize further needle sticks. If an IV catheter cannot be placed, and the participant agrees, standard venipuncture will be done to collect blood at baseline (fasting), and after 1- and 5 hours after eating the study product. If blood draws need to be repeated, the total amount of blood drawn for this study will not exceed 75 ml.

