Statistical analysis: Based on means and standard deviations observed in previous similar studies, our primary outcome will have in excess of 80% power to detect statistical significance among the study groups testing at the 5% level of significance. This calculation assumes that we have at least n=9 subjects in each of our four combinations of gender and blueberry status. This being the case, we propose to recruit n=11 subjects in each combination of gender and blueberry status (n=44 total, 22 per study arm) to compensate for a reasonable level of dropout that may occur. Power and sample size calculations were performed by SAS 9.4 Proc Power. [name], ACNC statistician will be in charged randomization process. Prior to analyses, data will be checked for potential outliers and aberrant measurements. Additionally, the data will be also checked for conformity with distributional assumptions of the proposed statistical models. Analysis of variance (ANOVA) or its non-parametric variants will be used to assess differences among gender and blueberry diet combinations. Significance will be declared at the 5 percent level of significance. To learn whether peak VO2 indeed modifies the effect of WBB supplementation, the potential modifier will be added into the ANOVA thus making an analysis of covariance (ANCOVA). The slope of the modifier will be allowed to depend on WBB status; that is, there will be a slope for the placebo group and one for the WBB group.

Reimbursement

The compensation per visit are \$50 for visit #1, \$50 for visit #2, and \$175 for visit #3 (Total \$275). If the participant decides not to complete the study, is unwilling, or unable to complete an assessment, a \$25 gift card or check will be provided.

In the event that blood draws or other measurements need to be repeated and rescheduled due to technical problems (but not participant refusal to blood draw), an additional \$50 gift card or check will be provided.

Ethical Considerations

This study will be conducted in accordance with all applicable government regulations and University of Arkansas for Medical Sciences (UAMS) research policies and procedures. This protocol and any amendments will be submitted and approved by the UAMS Institutional Review Board (IRB) to conduct the study. Formal consent and assent,

using the IRB-approved consent/assent form, will be obtained before the subject is

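### The ANOVA names no response and no visit 2 covariate, so outcomes measured at both visits lose precision whenever the visits are moderately correlated

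*Combined protocol and SAP*

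**What the plan says.** The whole analysis plan is one paragraph under Data Analysis. For the main comparison: "Analysis of variance (ANOVA) or its non-parametric variants will be used to assess differences among gender and blueberry diet combinations". For effect modification by fitness, peak VO2 joins the same model with a separate slope in each arm. The paragraph names no response variable and no term for the visit 2 value.

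The analysis serves two aims listed under Objectives: "Assess the effects of short-term wild blueberry supplementation on immune responses as well as on markers of bone metabolism and cardiovascular health", and "Evaluate if cardiorespiratory fitness (peak VO2) modifies the association between blueberry derived polyphenol consumption and markers of cardiovascular health".

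Measurements at both visits are described elsewhere:

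- **FMD** (Endothelial function): measured fasted at visits 2 and 3, and again after product at visit 3 only.
- **Blood pressure** (Vital signs): "Blood pressure, heart rate, and body temperature will be assessed using standard techniques at each visit".
- **Blood** (Blood Collection): "At visit #2, up to 16 ml (3.25 teaspoons) of whole blood will be collected following an overnight fasting", and "At visit #3, up to 24 ml (~1.6 tablespoons) of blood will be collected in the fasting state (baseline". Whether a given marker is assayed is left open, because that section says what plasma and serum may be used for.
- **Urine**: collected at both visits.

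Study product "will be consumed starting on the day of study visit #2 until the morning of visit #3". That visit 2 measurements come before that day's product is implied by the fasting requirement but not stated.

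**The concern.** Without the visit 2 value in the model, stable differences between children stay in the error term. Sex-by-arm cells remove only the part due to sex. The trial recruits all BMIs, and the protocol itself notes that puberty strongly affects bone turnover. With about 36 evaluable children this can cost appreciable power.

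The two obvious unadjusted responses fail at opposite ends. Visit 3 values lose most when the visits are highly correlated; change scores lose most when the correlation is low. ANCOVA needs no advance knowledge of the correlation.

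The unnamed response also leaves a choice open until the data are seen. And the only blood sample labelled as baseline is the visit 3 fasting draw. It follows days of product, so it cannot serve as the baseline for the 6-day effect.

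**Working it through.** **Inputs from Data Analysis.** Four sex-by-arm cells; at least 9 children per cell assumed for power (4 × 9 = 36); 11 per cell recruited (4 × 11 = 44); 5% level, taken as two-sided; power above 80% for a primary outcome that the section does not name.

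**Assumptions.** Between-visit correlation ρ = 0.3, 0.5, 0.7; equal SD at both visits; normal errors. The 1-df arm contrast is this review's choice. The documents supply none of these.

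**The plan's own figure.** Power above 80% cannot be reproduced, because no mean, SD or effect size is given. The illustration is therefore anchored at exactly 80% power on visit 3 values.

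**1. Visit 3 values.** For difference d (in SD units) and variance factor v, the noncentrality is λ = N·d²/(4v). With N = 36, v = 1, 1 and 32 df, 80% power requires d = 0.963, so λ = 36 × 0.963²/4 = 8.35.

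**2. Change from visit 2.** v = 2(1−ρ) = 1.4, 1.0, 0.6, with 32 error df. A two-visit repeated-measures ANOVA tests arm-by-visit identically, so that reading is covered too.

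**3. ANCOVA on the visit 2 value.** v = (1−ρ²)(1 + F/32), with F distributed as F(1,32) to allow for chance imbalance, and 31 error df. F/32 has mean 1/30, so v averages 0.91 × 31/30 = 0.940, 0.75 × 31/30 = 0.775 and 0.51 × 31/30 = 0.527. Power is averaged over F.

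| 1-df arm contrast, d = 0.963 | ρ = 0.3 | ρ = 0.5 | ρ = 0.7 |
|---|---|---|---|
| Visit 3 values, power | 80.0% | 80.0% | 80.0% |
| Change, power | 65.8% | 80.0% | 95.1% |
| ANCOVA, power | 82.3% | 88.8% | 97.1% |
| Change, detectable d at 80% | 1.140 | 0.963 | 0.746 |
| ANCOVA, detectable d at 80% | 0.935 | 0.849 | 0.700 |

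**4. Four-cell test**, closer to the plan's wording: same d, 3 numerator df. Visit 3 values give 62%; change 46%, 61%, 85%; ANCOVA (simulated) 64%, 74%, 90%.

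**5. Peak VO2-by-arm slope difference** (simulated), set at 80% on visit 3 values, which needs 1.09 SD per SD of peak VO2: change 67%, 80%, 94%; ANCOVA 82%, 88%, 96%. Simulated type I error was 0.049 to 0.051 for all models.

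**6. In terms of sample size.** At d = 0.963, visit 3 values in all 44 recruits give 87.6%. ANCOVA at ρ = 0.5 in 36 children gives 88.8%.

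**7. Where ANCOVA does not win.**

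- Against visit 3 values it breaks even at ρ = 0.184. Below that it is slightly worse: 79.0% at ρ = 0.1 and 78.6% at ρ = 0.
- Against change, ignoring the one error df, the factors are equal when 2(1−ρ) = (1−ρ²) × 31/30, so ρ = 60/31 − 1 = 0.935. Above that it is marginally worse (detectable d of 0.306 against 0.305 at ρ = 0.95).

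**The case against.** The strongest reply is that silence is not exclusion. The paragraph is compatible with change from visit 2 or a repeated-measures ANOVA, both of which use the visit 2 value. This stands as a description of the text, but both readings reduce to the change score, which ANCOVA beats at all three assumed correlations.

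Second, the gain over whichever unadjusted response turns out better is modest: 2.3 points at ρ = 0.3, 8.8 at 0.5, where it peaks, and 1.9 at 0.7. Larger gaps arise only against the worse response. That is correct, but the better one cannot be picked without knowing ρ.

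Third, the plan's power statement belongs to an unnamed primary outcome. If that is an objective 1 metabolite, this point does not touch it. That also stands, and it is why the power figures are illustrations only.

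Fourth, a child lacking only the visit 2 value drops out of a standard ANCOVA but stays in a visit 3 analysis. If two of 36 were lost this way, ANCOVA power would be 79.8% at ρ = 0.3, which removes the gain, and 86.8% at ρ = 0.5. Change scores lose the same children. The fix should cover this, the timing of blood pressure, and a counterpart for the non-parametric option.

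Finally, the baseline label in Blood Collection most naturally means pre-dose for the hourly draws. Nothing suggests another intent; a clarifying sentence is enough.

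**Conclusion.** The concern holds. The plan names neither a response nor a visit 2 term, although the measurements for adjustment are already scheduled. This is lost efficiency, without bias, and an unadjusted analysis would remain valid. The change should be made, but validity does not depend on it.

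At correlations from 0.3 to 0.7, the gain in the arm contrast is about 2 to 17 points over visit 3 values and about 16 to 2 points over change. The worst loss against visit 3 values is 1.4 points, at zero correlation. The sizes rest on the assumed correlations, normal errors and 36 children with both values. FMD and blood pressure are certain to be measured at both visits; blood markers qualify only where both samples are assayed.

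**What to change.** Prespecify, for continuous fasting objective 2 outcomes measured or assayed at both visits (FMD, blood pressure, and blood, immune or bone markers where both samples are assayed):

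> Response: visit 3 fasting value. Model: ANCOVA with arm, sex, arm-by-sex and the visit 2 value as covariate. Visit 2 samples, FMD and blood pressure are taken before the first product and are the baseline for the 6-day effect. In the peak VO2 effect-modification model for the same outcomes, the visit 2 value is included beside peak VO2 and peak VO2-by-arm.

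Three short additions complete it:

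- A rule for a missing visit 2 value, such as imputing the overall mean without regard to arm, so that the child stays in the analysis.
- A baseline-adjusted counterpart for the non-parametric option, such as ANCOVA on ranks.
- A sentence that the visit 3 fasting value is the pre-dose reference for the 1 to 5 hour response only.

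Do not extend the model to objective 1 metabolites, where the visit 2 value after a low-polyphenol diet may predict visit 3 weakly, to microbiome, metabolomics or sequencing outcomes, or to anything assayed at one visit only.

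The cost is analysis wording, confirmation by the investigators that visit 2 measurements do precede the product, and one error degree of freedom. If the visits were uncorrelated, power would fall from 80.0% to 78.6% for the arm contrast, and by a similar amount in the peak VO2 model. No new visit, sample or assay is requested.
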